We will select two sets of signal processing parameters that either provide a high level of signal manipulation (with concomitant improved audibility) (Fitting A) or a low level of signal manipulation (Fitting B). We will select signal processing (combinations of WDRC, frequency compression) that produce either high levels of signal manipulation or low levels of signal manipulation; that is, that represents a situation of more or less signal manipulation, with corresponding variability in patient response. Note that our goal here is simply to select processing choices that suit the experimental hypothesis; we are not interested in making recommendations about specific algorithm parameters (e.g., frequency compression); rather, we are interested in testing the idea that listeners respond differently to the net effect of signal manipulation and that those responses are related to patient factors including cognition. All hearing aid parameters will be constrained such that the signal is audible, comfortable, and clinically realistic (based on the range of available fitting parameters).

We will obtain hearing aids for use in the trial. We will choose the specific hearing aids based on the technology available at the time of the trial. Commercial hearing aids universally offer noise suppression and WDRC. We anticipate that twelve individuals (fit binaurally = 24 aids, with 4 aids held for backup) will be enrolled at a time. Each individual will wear one processing condition for 6 weeks, followed by the other for 6 weeks, for a total 12-week trial. Order of the processing conditions will be counterbalanced across subjects. Allowing for transition time (to order earmolds, program hearing aids, etc.) we anticipate testing 36 individuals per year and completing the target sample of 45 subjects in <1.5 years. Fitting procedure will follow accepted clinical protocol. Briefly, we will program each hearing aid to NAL-NL frequency-gain response, plus the desired features (e.g., frequency lowering, noise reduction, WDRC release time). Real-ear aided response will be measured with a probe microphone system and frequency-gain response adjusted to meet prescribed NAL-NL targets. Each

HA outcomes in Older Adults:

participant will be tested at the hearing aid fitting and again and 6 weeks post-fitting. During that time they will wear the hearing aids in their own environment.

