Outcomes. Two important goals in hearing-aid processing are to improve speech intelligibility and quality.

Speech intelligibility. Speech intelligibility will be tested using low-context (IEEE⁵¹) sentences in quiet and in babble at a range of signal-to-noise ratios (SNRs). The processing will be provided by the settings of the wearable hearing aids; and the patient will be aided binaurally. Subjects will be tested in a double-walled sound booth with the test signal (conversational speech level) presented through a speaker. The speaker will be positioned at a typical conversational distance (approximately 1m) and azimuth (0°) and the subject will respond by repeating the sentence heard. The hearing aid will be programmed by the research audiologist. Both the research assistant (who will conduct the speech tests) and the patient will be blind to the processing condition. Based on our previous data and on desire to sample realistic listening conditions we expect to use SNRs ranging from 0 to +10 dB. Our protocol for measuring speech intelligibility is as follows. The listener is seated in a double-walled sound booth and speech is presented to the listener at conversational levels in free field. Speaker distance (~ 1 m) and azimuth (0°) mimic a conversational situation. A locally-developed Matlab interface allows the listener to signal for presentation of the next sentence and for scoring of correct repetition of key words by an experimenter seated outside the sound booth. To confirm reliable scoring, an audio file of the listener's response is digitally stored and rescored by a second tester who is blinded to the initial scoring.

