Each subject will receive a study code and that code will be used for all study data. The link between the subject name and code are password-protected and stored on a HIPAA-approved server with server security managed by Northwestern School of Communication computer support staff. All research staff will be trained in appropriate Human Subjects protection procedures, including confidentiality. Data is accessible only to study staff via password-protected files. Additionally subject data may be shared with collaborators at the University of Colorado Boulder. When sharing information will be exchanged via secure FTP. All (de-identified) data will be stored in a secure database accessible via password by study staff at either

HA outcomes in Older Adults:

site. Weekly meetings across sites will include discussion of subject confidentiality. All personnel involved at either site will complete appropriate Human Subjects Protection training. Any unanticipated problems will be reviewed by the PI and reported as required.

Withdrawal of Subjects

Subjects are free to discontinue testing at any time at any point of the study, for any reason. All testing will be done in a manner to ensure safety of our subjects (e.g presenting sounds at a comfortable listening level) If a subject decides to withdraw from the research study only the data collected up to that point will be used with their permission. If they do not provide their permission their data will be withdrawn completely. A participant may be removed from the study if they lose or damage the study aids, do not wear the study aids for more than 6 hours a day, or are unable to adhere to the prescribed study schedule and tasks. In the event that a participant is removed from the study without their consent compensation will be pro-rated based upon the duration the participant remained compliant with study tasks and procedures. Once a participant is unable to continue with the study, compensation will end.

Statistical analysis plan

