Outcome measures between the optimal and suboptimal conditions will be compared using a paired t-test. We expect customized processing settings, which will utilize our cognitive and peripheral test batteries, will result in statistically significant and clinically meaningful improvements when compared to traditional fittings. We will identify any acclimatization effects by monitoring changes in outcomes observed over time. All subjects are expected to fully acclimatize to the hearing aid device by the end of the six-week trial. We will use a paired t-test analysis to compare the outcomes between the “high modification” and “low modification” conditions. This experiment will be powered to detect mean differences of 0.5 standard deviations with a sample size of 45 at 90% power and $\alpha=0.05$.

Sharing of Results with Subjects

Results of standard clinical procedures (e.g auditory testing) will be made available to participants at their request. Participants often have questions about their hearing and hearing aids. Counseling and recommendations will be done by or under the supervision of [name] the study PI and clinical audiologist. If research participants request the results from the research testing or cognitive testing, these results will be provided to the participant with the explanation that they are for “research purposes only” and not meant as a diagnostic tool or clinically reliable.

Recruitment Methods

Individuals in our lab subject pool who have expressed an interest in future studies will be contacted by phone or email (whichever they have indicated as a preferred contact) by the PI or her research assistant. Additional subjects will be recruited as needed by: (a) Flyers posted in our clinic and on community bulletin boards (b) Letter to potential participants. These letters will be sent to potential participants in the Aging Research Registry and the Northwestern University Audiology Clinic (c) newspaper advertisements

Subjects will receive \$10 per hour for participation. Participants will receive a bonus payment of \$40 after 6 weeks of wearing Fitting A, and \$50 after 6 weeks of wearing Fitting B. Therefore in experiment 2, a subject will be paid \$250 if they complete all study visits/tasks. (8 study visits lasting 2 hours paid at \$10/hour: \$160 + bonus payments of \$40 and \$50 = \$250 total)The

HA outcomes in Older Adults:

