subject is paid by check or cash. Typically this is done at the end of each study visit (for multiple visits), but some subjects opt to receive a single payment at completion of the entire study. We follow the subject's preference in this matter. The subject will be asked to sign a receipt verifying that they have received payment. A subject who withdraws from the study retains the amount paid for the portions of the study that were completed, but forfeits pay for the uncompleted portions of the study. Potential subjects will not be paid for the hearing test which is done to determine whether criteria for participation has been met.

Provisions to Protect the Privacy Interests of Subjects

During the consent process a lab member will explain that their identifiable information will not be used. Each participant will receive a study code that will be used for all study data. The only link between identifiable data and a study code will be on a password protected HIPAA-approved server with server security managed by Northwestern School of Communication computer staff. Before starting a study procedure the lab member will explain the task and reiterate that they are free to stop at any point. During the administration of questionnaires or cognitive testing the tester will remind the subject they can decline to answer any question they feel uncomfortable answering without any negative consequences.

Consent Process

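### Read with the plan's own definition of Fittings A and B, the first bonus (40 or 50 dollars) depends on the blinded processing condition: a potential, not demonstrated, blinding leak

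*Combined protocol and SAP*

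**What the plan says.** All references are to the combined protocol and SAP.

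- **Hearing aid fitting** defines the letters. The two parameter sets "provide a high level of signal manipulation (with concomitant improved audibility) (Fitting A) or a low level of signal manipulation (Fitting B"). Each is worn for 6 weeks, and "Order of the processing conditions will be counterbalanced across subjects". A is therefore not always the first fitting.
- **Outcomes, Speech intelligibility** sets the blinding: "Both the research assistant (who will conduct the speech tests) and the patient will be blind to the processing condition". On who sets up the devices it says: "The hearing aid will be programmed by the research audiologist". The audiologist is not listed as blinded.
- **Recruitment Methods** gives 10 dollars an hour for 8 visits of 2 hours, plus 40 dollars "after 6 weeks of wearing Fitting A" and 50 dollars "after 6 weeks of wearing Fitting B", for a total of 250 dollars. On the timing of payment it says: "Typically this is done at the end of each study visit (for multiple visits"). Some participants take a single payment at completion instead. A receipt is signed, and a participant who withdraws keeps what was paid for the parts completed.
- **Withdrawal of Subjects** says that, for participants removed from the study, "compensation will be pro-rated based upon the duration the participant remained compliant with study tasks and procedures".

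No section redefines A and B as first and second fitting, and no section says who sets or hands over the payment.

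**The concern.** A payment made during a blinded crossover should not vary with the blinded condition. Here, on the plan's own definition of the letters, it does. After the first six weeks, the amount separates participants who wore the high-manipulation fitting from those who wore the low-manipulation fitting. By elimination it also shows which one comes next. The protocol holds both pieces needed to decode the amount: the bonus schedule and the meaning of the letters. Someone who knows the protocol and sees the first bonus could infer the condition before the second period.

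The second-period measurements would be at stake. If the speech tester drew the inference, the live scoring of key words would be exposed. If the participant did, the self-reports would be exposed: quality ratings, EAR, SSQ and reported hours of use.

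**Working it through.** **Inputs.** From Recruitment Methods: 10 dollars an hour, 8 visits, 2 hours each, bonuses of 40 (A) and 50 (B), stated total 250. From Hearing aid fitting: two orders, A then B and B then A.

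**Reproducing the plan's total.** Visits: 8 × 2 × 10 = 160. Total: 160 + 40 + 50 = 250 dollars, as stated.

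**Bonus by order, under each reading of the letters.**

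| Reading | Order | First bonus | Second bonus | Total |
|---|---|---|---|---|
| Letters are conditions | A then B | 40 | 50 | 160 + 40 + 50 = 250 |
| Letters are conditions | B then A | 50 | 40 | 160 + 50 + 40 = 250 |
| Letters are first and second fitting | either | 40 | 50 | 160 + 40 + 50 = 250 |

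On the condition reading, the first bonus differs by 50 − 40 = 10 dollars according to condition. On the period reading it is 40 dollars for everyone and carries no information. The total is the same throughout, so it cannot show which reading was intended.

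**What has to be true for someone to learn the condition.**

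1. The bonus is paid by condition, as the definition of the letters implies.
2. It is paid during the trial, which the plan calls typical, and not once at the end.
3. The person sees the amount and knows that it is tied to the letters.
4. The person also knows that A is high and B is low manipulation.

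Staff who know the protocol meet the knowledge parts of steps 3 and 4, because both facts are written in it. Whether such staff include the speech tester, and whether that person sees the payment, is not stated. For participants, neither part can be established. The consent pages are not available, so it cannot be checked whether they give the bonus by letter. A participant who knew only the schedule would learn a letter, not a processing level.

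**Early withdrawal, condition reading only.** Two people who each complete just the first six weeks would keep bonuses of 40 and 50 dollars for the same time in the study. This is a payment inconsistency, not a threat to validity.

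**Analysis.** The paired t-test, the sample size of 45 and the 90% power do not use the payment schedule, so none of them changes.

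**The case against.** The strongest reply is that the payment text simply means first and second fitting. A bonus that rises from 40 to 50 dollars looks like an ordinary completion incentive. The pro-rating rule for removed participants runs on duration, which suits a bonus by period better than one by condition. The payment paragraph also speaks of an experiment 2 that appears nowhere else, which suggests wording carried over loosely. This reading is plausible and may be what was done. It removes the disclosure, but it leaves A and B used in a sense that conflicts with their only definition, so the sentence still needs correcting.

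The reply can also point to limits on the damage. The audiologist who programs the aids could set the amount without involving any blinded person. Payment at the end of a visit comes after that visit's measurements. Quality ratings and questionnaires are entered by the participant, use is also datalogged, and speech responses are rescored from audio by a second tester. These points stand, with one reservation: the second tester is said to be blind to the first scoring, not to the condition.

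A reader might go further and infer that the blind is broken, or that participants are told their condition by the size of the payment. The documents do not support that. They do not show that any blinded person has both the schedule and the meaning of the letters, or that the tester handles payment. A reader might also infer that the 10 dollar gap gives unequal incentives to wear the two fittings. Nothing in the documents shows such an effect, and none is claimed.

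**Conclusion.** The point holds as a minor one. On the only definition of Fitting A and Fitting B in the documents, the first bonus is 40 or 50 dollars according to a condition that the plan keeps from the patient and the speech tester. That is an avoidable link between payment and a blinding safeguard. It is potential, not demonstrated, and it concerns mainly staff who know the protocol and see the payment before the second period.

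The conclusion assumes that the letters in the payment text carry their defined meaning and that the bonus is paid during the trial. If the letters meant first and second fitting, only a labelling conflict remains. For participants who take a single payment at completion, the early disclosure does not arise. The number of people affected and the size of any bias cannot be derived from the documents.

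**What to change.** Under Recruitment Methods, state that the bonus is 40 dollars after the first 6-week period and 50 dollars after the second, whichever fitting is worn. Keep A and B for the processing conditions only.

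Both orders are then paid 40 followed by 50, and the total stays 160 + 40 + 50 = 250 dollars. Anyone who leaves after the first period keeps the same bonus. The cost is one sentence. Whether a participant-facing document needs the same edit cannot be checked here.
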